### **15.6 Risk to Benefit Rationale**

A thorough risk assessment was completed, applicable control measures were applied, and analysis confirmed that there are no unacceptable residual risks. Based on the risk management review and with management approval of the residual risks, the device design, device usability, and manufacturing process of the JETi Catheter has an acceptable level of risk for its intended use.

The JETi system is an FDA-cleared device and a part of the current standard of care for clot removal in the peripheral vasculature.

Use of the JETi System for mechanical thrombectomy may allow for thrombus removal without the use of thrombolytic drugs with an acceptable device-related serious adverse event rate. Taking these into consideration, the clinical benefits that may be expected from the removal of emboli and thrombus from the peripheral vasculature with the JETi System outweigh the possible risks that patients may experience when participating in this clinical investigation.

## APPENDIX I: ABBREVIATIONS AND ACRONYMS

Acronym or Abbreviation	Complete Phrase or Definition
AE	Adverse Event
ABI	Ankle Brachial Index
aPTT	Activated Partial Thromboplastin Time
BUN	Blood Urea Nitrogen
CDT	Catheter-Directed Thrombolysis
CEAP	Clinical-Etiologic-Anatomic-Pathologic
CFR	Code of Federal Regulations
CIP	Clinical Investigation Plan
CRF	Case Report Form
DVT	Deep Vein Thrombosis/Deep Venous Thrombosis
EC	Ethics Committee
eGFR	Estimated Glomerular Filtration Rate
EDC	Electronic Data Capture
FDA	Food and Drug Administration
GCP	Good Clinical Practice
HIPAA	Health Insurance Portability and Accountability Act Intersocietal Commission for the Accreditation of Vascular
ICF	Informed Consent Form
IFU	Information for Use
INR	International Normalized Ratio
IRB	Institutional Review Board
IVC	Inferior Vena Cava
JETi	JET Enhanced Thrombectomy intervention
LMWH	Low Molecular Weight Heparin
PT	Prothrombin Time
PTS	Post Thrombotic Syndrome
QOL	Quality of Life
SAE	Serious Adverse Event
SAP	Statistical Analysis Plan
SDU	Saline Drive Unit
SF-12	Short Form-12
US	United States

## APPENDIX II: DEFINITIONS

### Amputation

The removal of a body extremity by surgery. For this study, the definition of amputation will only apply to amputations of the limb that was treated.

Minor amputation: amputation below the ankle

Major amputation: amputation above the ankle

### Ankle Brachial Index (ABI)

The ABI is the ratio of the ankle to arm pressure, and it is calculated by dividing the higher systolic blood pressure of the two arteries (Dorsalis pedis or Posterior tibial) at the ankle of the assessed leg by the higher of the two brachial systolic blood pressures.

Calculation of the Ankle Brachial Index:

$$\text{ABI} = \text{Highest Ankle Systolic Pressure} / \text{Highest Brachial Systolic Pressure}$$

### Death (per ARC 1)

When possible, death will be classified according to underlying cause. Death within 30 days of the study procedure will be classified as procedure related unless medical history or autopsy findings demonstrate otherwise.

#### ***Cardiac death:***

Any death due to proximate cardiac cause (e.g., MI, low-output failure, fatal arrhythmia), unwitnessed death, or death of unknown cause.

#### ***Vascular death:***

Death caused by noncoronary vascular causes, such as cerebrovascular disease, pulmonary embolism, ruptured aortic aneurysm, dissecting aneurysm, or other vascular diseases.

#### ***Non-cardiovascular death:***

Any death not covered by the above definitions, such as death caused by infection, malignancy, sepsis, pulmonary causes, accident, suicide, or trauma.

### Dissection

National Heart, Lung, and Blood Institute (NHLBI) Dissection Classification System:

- A. Minor radiolucencies within the lumen during contrast injection with no persistence after dye clearance.
- B. Parallel tracts or double lumen separated by a radiolucent area during contrast injection with no persistence after dye clearance.
- C. Extraluminal cap with persistence of contrast after dye clearance from the lumen.
- D. Spiral luminal filling defects.
- E. New persistent filling defects.
- F. Non-A-E types that lead to impaired flow or total occlusion.

Note: Type E and F dissections may represent thrombus.

### Lower Extremity Deep Vein Thrombosis or Deep Venous Thrombosis (DVT)

DVT occurs when a blood clot forms in a deep vein, usually in the lower leg, thigh, or pelvis, but it can also occur in the arm.

For this study, the definition of Lower Extremity Deep Vein Thrombosis will apply to lower extremity venous thrombosis involving the femoral, common femoral, or iliac veins, or popliteal, or inferior vena cava (IVC) alone or in combination.

Acute clot for this study is defined based on signs and symptoms of onset of <2 weeks

Subacute clot for this study is defined based on signs and symptoms of onset of 2-6 weeks

Chronic clot for this study is defined based on signs and symptoms of onset of >6 weeks.

### **Major Bleeding**

- **BARC IIIa:** Overt bleeding plus hemoglobin drop of 3 to < 5 g/dL (provided hemoglobin drop is related to bleed); transfusion with overt bleeding or
- **BARC IIIb:** Overt bleeding plus hemoglobin drop  $\geq$  5 g/dL (provided hemoglobin drop is related to bleed); cardiac tamponade; bleeding requiring surgical intervention for control; bleeding requiring IV vasoactive agents
- **BARC Va:** Probable fatal bleeding; no autopsy or imaging confirmation but clinically suspicious or
- **BARC Vb:** Definite fatal bleeding; overt bleeding or autopsy, or imaging confirmation

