## 4.0 ENDPOINTS

### 4.1 Primary Endpoints

#### 4.1.1 Arterial Subjects

For subjects treated for arterial thrombosis (may include diagnoses such as acute limb ischemia, chronic limb ischemia/chronic limb threatening ischemia, peripheral artery disease, etc.) or arteriovenous (AV graft, AV fistula) thrombosis, all endpoints are descriptive.

There will be no hypothesis testing, and there are no statistical power considerations. For subjects treated for arterial or arteriovenous thrombosis, the primary endpoints are:

- **Clot removal grade** for each JETi-treated target vessel(s) from pre-JETi angiogram to post-JETi angiogram (post-JETi thrombectomy and prior to any adjunctive therapies to treat underlying culprit lesions) per the grades in **Table 1** (vessel basis). The independent imaging core laboratory will be responsible for assessing this endpoint.
- **Composite of JETi-related major adverse events (MAEs)**, defined as the following JETi-related events: device-related death, major amputation of the treated limb (arterial subjects only),

or major bleeding up to 30 days post-JETi procedure and as adjudicated by a clinical events committee (CEC) (subject basis). Refer to **Appendix II** for definitions of major adverse events.

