#### 4.1.2 Venous Subjects

For subjects treated for lower extremity DVT, the primary endpoints are:

- **Percent of treated vessel(s) with  $\geq 75\%$  venous thrombus reduction** from pre-JETi venogram to final venogram (post-JETi AND after any/all adjunctive therapies to treat underlying culprit lesions) via modified Marder score. The independent imaging core laboratory will be responsible for assessing this endpoint.  
If no adjunctive therapies or devices are used after JETi, post-JETi modified Marder score is also final score.

- **Composite of JETi-related major adverse events (MAEs) up to 30 days post-JETi procedure**, defined as the following JETi-related events adjudicated by a clinical event committee (CEC):
  - 1) death,
  - 2) symptomatic pulmonary embolism (PE),
  - 3) major bleeding
  - 4) re-thrombosis of JETi-treated vessel(s).Refer to **Appendix II** for definitions of major adverse events.

 Refer to Appendix II for definition of Lower Extremity Deep Venous Thrombosis

Note, the effectiveness outcome for subjects treated for venous thrombosis that is not lower extremity DVT as defined in **Appendix II** (e.g., upper extremity DVT) will be assessed by clot removal grade, as defined in **Section 4.1.1**.

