## 6.0 TREATMENT AND EVALUATION OF ENDPOINTS

For this Registry, the following definitions apply:

- **Index procedure:** the entire intervention to treat the subject's peripheral vascular thrombosis. A subject's procedure may include more than one session if the subject is removed from the interventional suite and placed in a holding area with the intention of returning to the suite for additional treatments either the same day or following day (e.g., catheter placement or removal for CDT). An index procedure can start with JETi or any other treatment first.
- **Treatment:** the individual techniques performed during a procedure to address the subject's peripheral vascular thrombosis (e.g., JETi thrombectomy, balloon angioplasty, stent placement, or catheter-directed thrombolysis (CDT)). Note that "JETi treatment" will refer to treatment during which the JETi Thrombectomy device is used.

NOTE: A subject's treatment is determined by the treating physician based on the clinical situation and institutional practices.

- **Session:** a session is the in and out period within an interventional suite that a subject is receiving treatment. A subject's procedure may include more than one session if the subject is removed from the interventional suite and placed in a holding area with the intention of returning to the suite for additional treatments either the same day or following day (e.g., catheter placement or removal for CDT).

---

 Specifically Lower Extremity DVT subjects as defined in Appendix II

NOTE: Treatment for unexpected re-thrombosis is an adverse event and should not be considered as an additional session of the initial procedure.

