## **10.7 Clinical Events Committee (CEC)**

The Clinical Events Committee (CEC) is an independent adjudication body comprised of qualified physicians who are not participants in the clinical investigation. The CEC will review and adjudicate pre-specified events reported by investigators or identified by Safety personnel for the clinical investigation as defined in the CEC charter and according to definitions provided in this CIP.

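### Major bleeding in both primary safety composites has no intracranial criterion, so a survived JETi-related intracranial bleed without the listed features would not count as an MAE

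*Protocol*

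**What the plan says.** Protocol Appendix II, Major Bleeding, gives four classes:

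- BARC IIIa: "Overt bleeding plus hemoglobin drop of 3 to < 5 g/dL (provided hemoglobin drop is related to bleed); transfusion with overt bleeding".
- BARC IIIb: overt bleeding with a related hemoglobin drop of 5 g/dL or more, and "cardiac tamponade; bleeding requiring surgical intervention for control; bleeding requiring IV vasoactive agents".
- BARC Va, the first of two fatal classes: "Probable fatal bleeding; no autopsy or imaging confirmation but clinically suspicious".
- BARC Vb: "Definite fatal bleeding; overt bleeding or autopsy, or imaging confirmation".

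The arterial and arteriovenous composite (Protocol 4.1.1) consists of JETi-related device-related death, major amputation of the treated limb and major bleeding to 30 days. The lower extremity DVT composite (Protocol 4.1.2) lists death, symptomatic PE, "3) major bleeding" and re-thrombosis of a treated vessel, again JETi-related and to 30 days. Both sections send the reader to Appendix II for the definitions. Protocol 10.7 has the CEC adjudicate as set out in its charter and "according to definitions provided in this CIP". SAP 1.4.1 and 2.3.1 repeat the two composites and add no bleeding definition of their own.

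**The concern.** Appendix II mostly grades a bleed by blood loss, by the intervention it needed, or by death. An intracranial bleed can do grave harm without large blood loss, and it may be survived without transfusion, surgery or vasoactive drugs. If such a bleed occurred and were adjudicated JETi-related, the primary safety endpoint would not register it, while a transfused JETi-related access-site bleed would count.

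The setting makes the case relevant. Protocol 6.0 names catheter-directed thrombolysis among the treatments that may form part of the index procedure. In the 18-patient retrospective study cited in Protocol 1.0, 24% of procedures went on to overnight catheter-directed thrombolytics. The device's own indication (Protocol 2.2.2) includes infusing therapeutics, so a JETi-related adjudication is possible.

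The effect reaches one further endpoint. Procedural success, in both the arterial and the venous descriptive endpoints, is technical success without a JETi-related MAE within 5 days of registration or by discharge, whichever comes first. An event that is not an MAE cannot make the subject a procedural failure.

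**Working it through.** The plan has no figure to reproduce here. The check is to run one case through every criterion. The case is a non-fatal intracranial bleed within 30 days, adjudicated JETi-related, with no hemoglobin drop of 3 g/dL or more, no transfusion, no surgical control and no IV vasoactive agent.

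| Route to an MAE | Source | Met? |
|---|---|---|
| Overt bleed, related Hb drop 3 to <5 g/dL | Appendix II, IIIa | No |
| Transfusion with overt bleeding | Appendix II, IIIa | No |
| Overt bleed, related Hb drop ≥5 g/dL | Appendix II, IIIb | No |
| Cardiac tamponade | Appendix II, IIIb | No (different site) |
| Surgery for control | Appendix II, IIIb | No |
| IV vasoactive agents | Appendix II, IIIb | No |
| Probable or definite fatal bleeding | Appendix II, Va and Vb | No |
| Death | Protocol 4.1.1, 4.1.2 | No |
| Major amputation of the treated limb | Protocol 4.1.1 | No |
| Symptomatic PE | Protocol 4.1.2 | No |
| Re-thrombosis of a treated vessel | Protocol 4.1.2 | No |

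No route is met, so the case is outside both composites. If technical success was reached and no other MAE occurred in the window, the subject is a procedural success. A subject with a transfused JETi-related access-site bleed in the same window is a failure.

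The event is still recorded. Protocol 7.3.1 collects all SAEs and all device- and procedure-related AEs through 12 months. SAP 3.2 tabulates them by number of events and percentage of subjects, and Protocol 4.2.1 makes JETi-related AEs a CEC-adjudicated descriptive endpoint.

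Scale: one uncounted subject in a group of size n lowers the observed MAE percentage by 100/n points. Arterial and venous subjects are analysed separately (SAP 2.6), so the total of 280 is not a planned denominator, and the group sizes are not visible. Assuming 100 to 200 per group:

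- n = 100: 100/100 = 1.0 point.
- n = 200: 100/200 = 0.5 points.

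This is the effect of one event if it occurs. It is not an expected effect, because the documents give no frequency for such bleeds.

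**The case against.** The strongest reply is that the gap is narrow and the event is not lost. Only JETi-related, CEC-adjudicated events to 30 days count in either composite. A remote bleed attributed to a thrombolytic or an anticoagulant might not be judged JETi-related, and would then stay out even under a wider definition. An intracranial bleed would very likely meet the SAE criteria of Protocol 7.1.2 and be reported. The arterial endpoints are purely descriptive, so no decision there is shown to depend on one event. All of this stands, and it limits the size of the point. It does not repair the composite, because an SAE table does not correct a primary endpoint that omits the event.

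Four stronger readings are tempting, and the documents do not support them.

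- A reader might infer that the definition ignores bleeding site altogether. It does not, since cardiac tamponade is a site-specific item. The definition thus already accepts that location can make a bleed major without a hemoglobin threshold or transfusion, but only for the pericardium.
- A reader might infer that the registry would fail to capture such bleeds. Protocol 7.3.1 and SAP 3.2 show otherwise.
- A reader might infer that one event would decide success or failure. The success criteria are redacted. The 47-patient pilot in Protocol 1.0 reported no major adverse events through 30 days, but the protocol does not give that study's definition, so its zero is not a shown comparator.
- A reader might infer that the CEC could add the event on its own judgment, or equally that its charter forbids this. The charter is a separate document that was not available. What can be read is that the protocol's definitions bind the committee.

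**Conclusion.** The point holds in a narrow form. As written, Appendix II leaves a survived, JETi-related intracranial bleed within 30 days out of both primary safety composites when none of the listed features is present, and it allows that subject to be a procedural success. This follows from the list itself, which shows no sign of redaction, and it needs no outside bleeding scale.

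The size is 0.5 to 1.0 percentage points per uncounted subject, on assumed groups of 200 to 100. How often such a bleed would occur, and how often it would be adjudicated JETi-related, cannot be determined from the documents. The defect is in what the primary endpoint counts, and safety reporting is intact. It is worth correcting because the correction is cheap and uses data already being collected.

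**What to change.** Add intracranial bleeding, irrespective of hemoglobin drop, transfusion or intervention, to the Major Bleeding list in Appendix II. Both composites, their component summaries and procedural success then pick it up by reference. Align the CEC charter, and have the committee adjudicate the SAEs already collected to the amended definition before the primary analysis. If the omission is intended, the protocol should say so and give the reason.

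The cost is more than a line of text. It needs a protocol amendment with IRB/EC notification or approval (Protocol 10.2 and 12.1), some re-adjudication, and acceptance of a possibly slightly higher MAE rate. No new data collection is needed. The SAP's abbreviation list includes performance goal, but no use of it is visible. If a safety goal exists, the sponsor should confirm that its source used a comparable bleeding definition before widening this one.

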### **Pulmonary Embolism (per AHA)**

**Low-risk Pulmonary Embolism:** Acute PE and the absence of the clinical markers of adverse prognosis that define massive or submassive PE

**Massive Pulmonary Embolism:** Acute PE with sustained hypotension (systolic blood pressure <90 mm Hg for at least 15 minutes or requiring inotropic support, not due to a cause other than PE, such as arrhythmia, hypovolemia, sepsis, or left ventricular [LV] dysfunction), pulselessness, or persistent profound bradycardia (heart rate <40 bpm with signs or symptoms of shock).

**Sub-massive Pulmonary Embolism:** Acute PE without systemic hypotension (systolic blood pressure  $\geq$ 90 mm Hg) but with either RV dysfunction or myocardial necrosis.

- RV dysfunction means the presence of at least 1 of the following:
  - RV dilation (apical 4-chamber RV diameter divided by LV diameter >0.9) or RV systolic dysfunction on echocardiography
  - RV dilation (4-chamber RV diameter divided by LV diameter >0.9) on CT
  - Elevation of BNP (>90 pg/mL)
  - Elevation of N-terminal pro-BNP (>500 pg/mL); or
  - Electrocardiographic changes (new complete or incomplete right bundle-branch block, anteroseptal ST elevation or depression, or anteroseptal T-wave inversion)
- Myocardial necrosis is defined as either of the following:
  - Elevation of troponin I (>0.4 ng/mL) or
  - Elevation of troponin T (>0.1 ng/mL)

### **Renal Failure**

Acute renal failure, also known as acute kidney injury (AKI), definition as per Kidney Disease Improving Global Outcomes (KDIGO):

- Increase in serum creatinine of  $\geq$ 0.3 mg/dL within 48 hours or  $\geq$ 50% within 7 days OR
- Urine output of <0.5 mL/kg/hour for >6 hours

### **Symptomatic Pulmonary Embolism**

Define as per Society of Interventional Radiology (SIR) Quality Improvement Guidelines for the Treatment of Lower-Extremity Deep Vein Thrombosis with Use of Endovascular Thrombus Removal:

[figure not shown]
Episodes of DVT or PE can be symptomatic (the patient had symptoms and/or signs that prompted evaluation for DVT or PE) or asymptomatic (DVT or PE was detected on an imaging study in a patient without symptoms)

[figure not shown]
[figure not shown]

**APPENDIX III: RATES OF FORESEEABLE ADVERSE EVENT**

## APPENDIX IV: LABELING

Device labeling is available under separate cover.

## APPENDIX V: CASE REPORT FORMS

The Case Report Forms (CRF) will be provided under a separate cover.

## APPENDIX VI: INFORMED CONSENT FORM

A template Informed Consent Form (ICF) will be provided separately.

## APPENDIX VII: MONITORING PLAN

[figure not shown]
A copy of the Monitoring Plan can be obtained upon request from the Sponsor Clinical Project Manager for the Registry.

[figure not shown]
## APPENDIX VIII: ADDITIONAL DOCUMENTS

[figure not shown]
The following documents will be provided separately:

1. Quality of Life Survey (SF- 12)
2. Villalta Score for PTS Assessment
3. Core laboratory imaging guidelines

[figure not shown]
**APPENDIX VIII: REVISION HISTORY**

### APPENDIX IX: CIP SUMMARY

Clinical Investigation Name	JETi Registry
Title	JET Enhanced Thrombectomy Intervention Registry
Objective	To collect real-world data on the safety, performance, and clinical benefits of any JETi System for the treatment of thrombosis in the peripheral vasculature
Device	JETi System
Number of Subjects	Approximately 280 subjects
Clinical Investigation Design	A prospective, single-arm, multi-center, registry
Primary Endpoint(s)	
For subjects treated for arterial thrombosis:
 
 
• Clot removal grade for each JETi-treated target vessel from pre-JETi angiogram to post-JETi angiogram (post-JETi thrombectomy and prior to any adjunctive therapies to treat underlying culprit lesions) per the grades in Table 1. The independent imaging core laboratory will be responsible for assessing this endpoint.
 
• Composite of JETi-related major adverse events (MAEs), defined as the following JETi-related events: device-related death, major amputation of the treated limb (arterial subjects only), or major bleeding up to 30 days post-JETi procedure and as adjudicated by a clinical events committee (CEC). Refer to Appendix II for definitions of major adverse events.
 
 
For subjects treated for venous thrombosis:
 
 
• Percent of treated vessel(s) with <math>\geq 75\%</math> venous thrombus reduction from pre-JETi venogram to final venogram (post-JETi AND after any/all adjunctive therapies to treat underlying culprit lesions) via modified Marder score. The independent imaging core laboratory will be responsible for assessing this endpoint. If no adjunctive therapies or devices are used after JETi, post-JETi modified Marder score is also final score.
 
 
[REDACTED]
 
 
• Composite of JETi-related major adverse events (MAEs) up to 30 days post-JETi procedure, defined as the following JETi-related events adjudicated by a clinical event committee (CEC): death, symptomatic pulmonary embolism (PE), major bleeding, re-thrombosis of JETi-treated vessel(s). Refer to Appendix II for definitions of major adverse events.
 

Subject Follow-up	Office visits at 30 days, and 12 months post JETi procedure
Inclusion Criteria	
 
1. Subject was treated or is expected to be treated for acute/subacute thrombosis as determined by the investigator in the peripheral vasculature with any of the JETi Peripheral Thrombectomy System.
 
2. Subject must provide written informed consent.
 
3. Subject must be <math>\geq 18</math> years of age.
 

Exclusion Criteria	

1. Subject has previously been registered in the JETi Registry in the last 12 months unless treated in the contralateral limb/different anatomy; patients treated in the contralateral limb/different anatomy may be included when treated within the last 12 months.

2. Subject is currently participating in another drug or device clinical investigation.

3. Subject has active symptoms and/or a positive test result of COVID-19 or other rapidly spreading novel infectious agent within the past 20 days.

---------------------------	---

